*Examining disparity driven vergence as a potential
diagnostic test for mild traumatic brain injury (mTBI)*

NCT Number NCT03529799

1) **Protocol Title**

Examining disparity driven vergence as a potential diagnostic test for mild traumatic brain injury (mTBI)

2) **IRB Review History***

None.

3) **Objectives***

Specific Aim 1 (SA1): Determine the validity and safety of disparity driven vergence testing with a portable goggle system using a pseudorandom ternary sequence of frequencies on a group of normal subjects.

Specific Aim 2 (SA2): Determine the vergence testing control values using a portable goggle system using a pseudorandom ternary sequence of frequencies on a group of normal subjects.

Specific Aim 3 (SA3): Determine the vergence testing values with a portable goggle system using a pseudorandom ternary sequence of frequencies on a group of subjects with history of mild traumatic brain injury and compare this to values in normal subjects.

4) **Background**

Vergence eye movements for focusing on objects include either convergence, the coordinated movement of both eyes towards the midline, or divergence, the coordination movement of both eyes towards the periphery. These eye movements are thought to be controlled by complex neurophysiological mechanisms that can be susceptible to damage by traumatic brain injury. Known involved areas in vergence include the oculomotor nucleus, cerebellum, and visual association cortex (Conn 2016), all of which can sustain damage during head trauma.

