feasible, we propose a pseudorandom ternary sequence approach to frequency distribution during disparity driven vergence to allow rapid analysis over a wide range of frequencies. Essentially, a pseudorandom frequency distribution can help extrapolate data to a larger frequency data set. We will also be evaluating the safety and side effect profile of using the goggles using a medical symptom questionnaire.

5) **Inclusion and Exclusion Criteria**

Inclusion:

- Aged 18 or older
- Both females and males

Exclusion:

- Central processing disorder
- Impaired vision without corrective lenses (max 20/60 uncorrected)
- Moderate to severe hearing loss (>55dB PTA, <50% word identification)
- Vestibular disorder except for patients recruited for SA3
- History of ear surgery other than myringotomy with or without tube placement
- Pregnant women
- Prisoners
- Adults unable to consent

6) **Number of Subjects**

60 subjects – 30 normal controls (no mTBI), 30 patients with mTBI.

7) **Recruitment Methods**

Normal subjects will be recruited from a pool of patients from a population who are unaffiliated or affiliated with University of Miami and meet inclusion criteria and not excluded by exclusion criteria. The faculty and students of any University of Miami School will be recruited through advertising in e-mails. Emails will be sent to staff and faculty associated with the UM Clinical Research Building (CRB) that have their emails stored in the UM Outlook server. Subjects will not be paid to participate. Students and staff will be assured that their participation will have no effect on their school performance or grades.

8) mTBI patients will be recruited by convenience from a pool of patients with history of mTBI and no prior vestibular disorders that present to the UM CRB Otology Clinic of [name] (SA3)”. The determination of their fitness for participation will be made during [name] clinical history and physical by asking about the history of the head injury and past medical history.

9) **Study Timelines**

Vestibular tests will take 15 minutes.

10) **Study Endpoints**

Each participant’s study will be completed when they have completed the vergence testing and other vestibular tests. At that point, the data will be de- identified.

11) **Procedures Involved**

The study will be conducted in 2 phases in which each phase comprises of thirty participants.

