In the first phase, thirty participants without mTBI who meet the inclusion criteria and are not excluded will be chosen to participate. Participants will sign an informed consent document and undergo 1 session of vergence testing, along with a series of vestibular tests. After this testing, the data will be de-identified and will only be labeled with sex and age of patient.

In the second phase, thirty participants with mTBI who meet inclusion criteria and are not excluded will be chosen to participate. Participants will sign an informed consent document and undergo 1 session of vergence testing, along with a series of vestibular tests. After this testing the data will be de-identified and will only be labeled with sex and age of patient.

After the session, patients will be given a medical symptom/toxicity questionnaire (MSQ) to evaluate for any side effects.and the SCAT-5 questionnaire, which will evaluate their current symptoms.

For each vestibular test and data to be obtained, see table below:

Test	Activity	Outcome OR Ordinal Value
Vergence Pursuit	Focusing on object moving forward and backwards	0 - 100
Spontaneous Nystagmus	Focusing on an object	Normal / Abnormal (Side)
Saccades ~ Horizontal Random	Focusing on objects randomly in horizontal axis	Normal / Abnormal (Side)
Saccades ~ Vertical Random	Focusing on objects randomly in vertical axis	Normal / Abnormal (Side)
Smooth Pursuit Horizontal ~ 0.1 Hz	Tracking objects in horizontal axis, at 0.1 Hz	Normal / Abnormal (Side)
Smooth Pursuit Horizontal ~0.75 Hz	Tracking objects in horizontal axis, at 0.75 Hz	Normal / Abnormal (Side)
Smooth Pursuit Vertical ~0.1 Hz	Tracking objects in vertical axis, at 0.1 Hz	Normal / Abnormal (Side)

Smooth Pursuit Vertical ~0.75Hz	Tracking objects in vertical axis, at 0.75 Hz	Normal / Abnormal (Side)
Predictive Saccades	Tracking an object moving in predictable manner	Percent (%) Error
Antisaccade	Moving eyes away from visual onset	% Error
OKN (optokinetic nystagmus) Trapezoidal	Tracking moving field	Normal / Abnormal (Side)
Visual Reaction Time	Reaction time to object	Seconds
Saccades and Reaction Time	Reaction time to off-center object	Seconds
Auditory Reaction Time	Reaction time to sound	Seconds
Self-Paced Saccade	Saccadic motion between two fixed targets	0 - 100
Pupil Reflex	Normal light reflex	0 - 100
Subjective Visual Vertical	Ability to perceive subjective tilt	0 - 100

12) **Data Storage**

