The only data to be stored will be the results of the vergence tests and vestibular testing done during the two sessions. These results will be tied together by a subject number that will also link to the sex of the patient and age of the patient. No PHI that identifies any participant will be kept. All the previously described data will be stored on the PI's computer and used for analyses purposes in room 580 of the clinical research building at the University of Miami Medical Center located at [name]. It will be password protected, and unique identifiers used for subject protection. Data will not be distributed, except in the form of peer-reviewed publication or oral presentation maintain the confidentiality of the subjects.

13) **Data Management***

Group mean data and single subject design will be utilized. In the group mean data scoring on each of the sessions will be aggregated for each of the specific aims. First session scores will be compared to second session scores using standard statistical methods with significance defined as $p < 0.05$. For the single subject design the number of subjects for each vestibular tests for each aim who have a significant difference in scores between the first and second session will be calculated and analyzed with descriptive statistics. In this way the investigators can calculate the difference between each test on the two sessions for each protocol, as it is very possible that some tests may be significantly different between the sessions and some tests will not.

Data will be stored on the PI's computer and used for analyses purposes in room 580 of the clinical research building at the University of Miami Medical Center located at [name]. It will be password protected, and unique identifiers used for subject protection. Data will not be distributed, except in the form of peer-reviewed publication or oral presentation maintain the confidentiality of the subjects. . No PHI that can identify any subjects will be kept beyond the second session of testing.

14) **Withdrawal of Subjects**

Subjects can withdraw at any time but if they withdraw their data will not be used and they will be replaced in the study by a new subject.

15) **Risks to Subjects**

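### SA1's only safety measure is a symptom form given after the session, with no baseline; unless it asks solely about new or worse symptoms, it cannot isolate side effects

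*Combined protocol and SAP*

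**What the plan says.** - **Aim.** Section 3 sets SA1 as "Determine the validity and safety of disparity driven vergence testing with a portable goggle system", in a group of normal subjects. Section 6 plans 30 of them.
- **Instrument.** Section 4 says "We will also be evaluating the safety and side effect profile of using the goggles using a medical symptom questionnaire". No other safety measure is named.
- **Timing.** Section 11 gives each participant one session and then says "After the session, patients will be given a medical symptom/toxicity questionnaire (MSQ) to evaluate for any side effects". At the same point subjects receive "the SCAT-5 questionnaire, which will evaluate their current symptoms". Nothing is described before the session.
- **Analysis.** Section 13 compares first-session with second-session scores, and its single-subject count covers vestibular tests. It does not mention the MSQ, define a side effect or say how side effects are reported.
- **Withdrawals.** Under Section 14, the data of a subject who withdraws are not used and the subject is replaced.
- **Storage and completion.** Section 12 says "The only data to be stored will be the results of the vergence tests and vestibular testing done during the two sessions", a list without the MSQ or SCAT-5. Section 10 says each participant's "study will be completed when they have completed the vergence testing and other vestibular tests", with de-identification at that point and no mention of the questionnaires.

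**The concern.** A form completed once, after exposure, records whatever the subject feels then. If it asks about symptoms in general, a headache or eye strain present on arrival looks the same as one caused by the goggles. The safety half of SA1 would then report the prevalence of symptoms after the session, which is not the side-effect rate that Sections 3 and 4 promise.

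No other part of the plan supplies the missing contrast. The SCAT-5 is given at the same late point. Section 13's session comparison cannot serve, because Section 11 gives each subject one session. The mTBI group is no substitute, because SA1 concerns normal subjects. Nor can normal subjects be taken as symptom-free, because no criterion in Section 5 concerns current symptoms.

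**Working it through.** The plan states no side-effect rate, safety threshold or precision target, so there is no figure of its own to reproduce. The only input from the documents is n = 30 normal subjects (Section 6). Every rate below is an assumption.

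**Notation.** b = share with a symptom before the session; p = share of those still reporting it afterwards; i = share of symptom-free subjects who develop one; w = share of those with a baseline symptom who worsen (w ≤ p). Subjects whose baseline symptom resolves are taken to report none.

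- Post-session-only rate = b·p + (1 − b)·i
- New-or-worse rate = (1 − b)·i + b·w
- Excess = b(p − w), which is at most b

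**A. Goggles cause nothing and symptoms persist (i = w = 0, p = 1).** Expected reports = 30b; chance of at least one = 1 − (1 − b)^30.

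| b | Expected of 30 | Chance of at least one |
|---|---|---|
| 5% | 1.5 | 78.5% |
| 10% | 3 | 95.8% |
| 20% | 6 | 99.9% |

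At b = 10%, the expected post-only result is 3 of 30 (exact 95% CI 2.1% to 26.5%). A new-or-worse count would be 0 of 30 (0% to 11.6%) if no item fluctuated by itself between the two forms.

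**B. Some true effect (i = w = 5%).** The new-or-worse rate is 5% throughout.

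| b | Post-only, p = 1 | Excess (points) | Post-only, p = 0.5 | Excess (points) |
|---|---|---|---|---|
| 5% | 9.75% | 4.75 | 7.25% | 2.25 |
| 10% | 14.5% | 9.5 | 9.5% | 4.5 |
| 20% | 24% | 19 | 14% | 9 |

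Worked line, b = 10%, p = 1: 0.10 × 1 + 0.90 × 0.05 = 0.145; less 0.05 leaves 0.095.

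**C. Different truths give nearly the same result (p = 1).** With b = 10% and i = 10%, the post-only rate is 0.10 + 0.90 × 0.10 = 19% (5.7 of 30). With b = 20% and i = 0 it is 20% (6 of 30). A single post-session count of current symptoms cannot tell a 10% onset rate from none.

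**D. When the excess vanishes.** It is zero if b = 0, or if the form asks only about new or worse symptoms.

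**E. A bias the other way.** Suppose 31 normal subjects start testing and one stops because of a symptom. Under Section 14 that subject is dropped and replaced, so a true 1 of 31 is reported as 0 of 30.

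**The case against.** The strongest reply is in Section 11 itself. It gives the two forms different purposes, the MSQ for side effects and the SCAT-5 for current symptoms. That suggests the MSQ is meant to capture effects of the test, and it is a fair reason not to say that the plan can yield only a symptom rate. It is not proof, because a form's purpose does not show how its items are worded. The condition therefore stays in the conclusion.

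The second reply is that few controls will arrive with symptoms. Section 7 begins "Normal subjects will be recruited from a pool of patients", which alone could suggest a clinic sample. The sentence continues to people within or outside the university, and the route described is e-mail to faculty, students and staff. Section 5 also excludes vestibular disorder (apart from SA3 patients), central processing disorder, impaired vision and moderate to severe hearing loss. This stands: b may be near the bottom of the illustrated range, or below it.

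Third, the excess is never negative in this model, so a low post-only count would still reassure. That holds for the baseline problem alone. The withdrawal rule works in the other direction.

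Two stronger readings should be resisted. A reader might infer that a few pre-existing complaints would overturn the safety conclusion; the plan has no threshold or decision rule, so this cannot be shown. A reader might also infer from Section 12 that the safety forms are discarded. Section 22 keeps records in a locked file, Section 23 files the database with the other study materials, and nothing orders destruction. Loose drafting is the likelier explanation. De-identification also does not break the link between forms, because Section 12 keeps a subject number.

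**Conclusion.** The point holds conditionally. As described, the MSQ is given only after the single session, with no baseline and no counting rule. Unless its items are confined to symptoms that began or worsened with the test, it will overstate side effects by b(p − w), at most the baseline prevalence. Under the assumed 5% to 20% prevalence, persistent symptoms and no true effect, that is 1.5 to 6 spurious reports in 30. The excess is smaller if symptoms resolve and nil if the form already has the narrower wording. Even then, the missing rule for counting and reporting remains a gap.

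Severity is low to moderate. The weakness touches the safety half of SA1 and leaves the SA2 and SA3 vergence values alone. The storage list and the order of completion are drafting points only.

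**What to change.** **Section 11.** Give the same MSQ immediately before and immediately after the session, linked by subject number, and define a side effect as any item new or scored worse than before. If the form already asks only about new or worse symptoms, say so and omit the pre-session form.

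**Section 13.** Report the number and proportion of normal subjects with at least one new or worse symptom, with an exact (Clopper-Pearson) 95% CI. State the precision in advance: 0 of 30 leaves an upper limit of 1 − 0.025^(1/30) = 11.6%. Note that, without a control condition, the count also includes spontaneous fluctuation.

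**Sections 13 and 14.** For the safety count, keep subjects who withdraw after testing starts, where consent allows, and use all who started as the denominator.

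**Drafting.** Add the MSQ and SCAT-5 to Section 12's stored-data list. In Section 10, place completion and de-identification after the questionnaires. Align Section 11's labelling sentence, "After this testing, the data will be de-identified and will only be labeled with sex and age of patient", with the subject number in Section 12.

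**Cost.** Wording changes and at most one extra self-report form, assumed to take a few minutes on top of the 15 minutes of vestibular tests. No new staff or device is needed. The downside is that asking about symptoms beforehand may make some subjects more alert to them afterwards.

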Modern balance function assessment includes electronystagmography and more recently, videonystagmography (ENG/VNG) to assess vertigo, dizziness, and imbalance. Additionally, vestibular-evoked myogenic potentials (VEMP), rotational testing, and computerized dynamic posturography (CDP) are very useful in evaluating multi-sensory integration of vision, somatosensory, and vestibular system function. VNG records eye movements using digital video image technology employing infrared illumination to determine eye position. The use of VNG enables simultaneous subjective observation of eye movements together with objective data collection and analysis of eye movement waveforms via computer algorithms (Kang 2015). More recently vestibular function has been tested in rotational chair devices. These devices utilize VNG goggles and perform many of the same tests done in a traditional VNG test but adds tests that involve moving the body (and with the body the head) through a variety of motion paradigms. Eye response to these body/head accelerations are recorded and abnormalities can be plotted against established norms. This technology is useful but involves a large and expensive piece of equipment in a dedicated vestibular lab. As a result, portable devices have been developed that perform many of the same functions that the chair performs. Head to head comparisons between rotational chair testing and portable vestibulo-ocular reflex gain and phase testing have shown consistent results between modalities (Goebel 1995). Portable vestibular testing has thus become a reality, allowing physicians

and audiologists the ability to test subjects outside of the typical clinical setting and in a variety of environments and conditions.

As such portable devices arise and become available to practitioners, their safety, validity, and efficacy must be determined. The portable goggle system, IPAS goggles (Neuro-kinectics, Inc., Pittsburgh, PA), have been developed to measure vestibular function and can be used for vergence testing. Current tests of binocular disparity driven vergence examine only one frequency (0.1 Hz) and tests at that single frequency may provide only limited information in the diagnosis and follow-up of mTBI patients. A greater number of frequencies can provide a spectrum of values that may help with this assessment. As testing all of the possible frequencies is not

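### For SA2, Section 13 plans group means and counts of between-session change, but no measure of spread, no reference interval and no use of the stored age and sex

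*Combined protocol and SAP*

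**What the plan says.** Section 3 (Objectives) states SA2 as "Determine the vergence testing control values using a portable goggle system using a pseudorandom ternary sequence of frequencies on a group of normal subjects". SA3 then compares values in subjects with mTBI with those in normal subjects. The title begins "Examining disparity driven vergence as a potential" and continues by naming a diagnostic test for mTBI. Section 4 (Background), describing rotational chair testing, says that "abnormalities can be plotted against established norms".

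Section 5 admits anyone "Aged 18 or older", with no upper limit and no age strata. Section 6 gives the size: "60 subjects – 30 normal controls (no mTBI), 30 patients with mTBI". Section 11 (Procedures Involved) gives each participant one session, keeps sex and age with the data, and lists Vergence Pursuit on a 0 to 100 scale with no cut-off. Many of the other tests in that table are scored normal or abnormal.

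Section 13 is the only analysis text. It names two analyses. One is group mean data: "In the group mean data scoring on each of the sessions will be aggregated for each of the specific aims", with first-session scores compared with second-session scores at p < 0.05. The other is a single subject design, which counts the subjects whose scores differ significantly between the two sessions and summarises those counts descriptively. Age and sex are not mentioned there.

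**The concern.** If SA2's control values are to help in reading a diagnostic test, someone must be able to take one person's score and say whether it is usual for a normal adult. That needs the spread of individual scores and limits derived from it. A mean gives only the centre. The single subject analysis does not fill the gap, because it classifies change between sessions and not normality, and with one session per participant it has no data.

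Age and sex are kept with every result, and eligibility has no upper age limit, yet neither variable has a stated analytic role. If limits are wanted later, their form and their handling of age would be chosen after the data are seen. One of the three aims would then rest on an unplanned analysis.

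**Working it through.** The plan gives no SD, precision target or power, so there is no figure of its own to reproduce. Everything below is in SD units and assumes normally distributed scores.

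**Inputs from the documents.** n = 30 controls (Section 6; withdrawals are replaced under Section 14, so 30 is the analysed number); one session each (Section 11); score bounded 0 to 100 (Section 11); age and sex available (Sections 11 and 12).

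**1. What a group mean conveys.** The 95% CI half-width is t(0.975, 29)/√30 = 2.045/5.477 = 0.37 SD. The central 95% of individuals spans ± 1.96 SD. The share of normal individuals more than 0.37 SD from the mean is 2 × [1 − Φ(0.373)] = 0.71.

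**2. How precise a limit from 30 controls would be, without covariates.** SE of a 2.5% or 97.5% limit = √(1/30 + 1.96²/58) = √(0.0333 + 0.0662) = 0.316 SD. The 95% CI is ± 1.96 × 0.316 = ± 0.62 SD. A nominal 2.5% tail could then truly be anywhere from Φ(−1.96 − 0.62) = 0.5% to Φ(−1.96 + 0.62) = 9.0%. A nonparametric 2.5th percentile has rank 0.025 × 31 = 0.775, below 1, so 30 values cannot supply it.

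**3. Prediction factor with age and sex fitted.** Three coefficients leave 30 − 3 = 27 residual df, and t(0.975, 27) = 2.052. The factor is 2.052 × √(1 + h), where h is the leverage:

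- at the covariate means, h = 1/30: 2.052 × 1.0165 = 2.09
- at average leverage, h = 3/30: 2.052 × 1.0488 = 2.15
- at 1.5 SD from mean age, h = 1/30 + 2.25/29 = 0.111: 2.16
- the same, for one sex with sexes balanced and age unrelated to sex, h = 0.111 + 1/30 = 0.144: 2.19

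For comparison, t(0.975, 29) × √(31/30) = 2.08 is the factor for a plain mean with no covariates, so it should not be carried over to the regression.

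**4. Precision of the regression limits.** Replacing 1/30 by h and 58 by 2 × 27 = 54: at the covariate means, 1.96 × √(0.0333 + 0.0711) = ± 0.63 residual SD. At h = 0.144 it is 1.96 × √(0.144 + 0.0711) = ± 0.91 residual SD. The limits are therefore least certain at the ends of the age range.

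**5. Illustration of why age should be examined.** The documents do not say whether vergence changes with age, so the correlations here are assumptions. Suppose one lower limit at −1.96 SD served all ages. With correlation −0.5, it would flag Φ((−1.96 + 0.75)/0.866) = 8.1% of normal people 1.5 SD older than average and Φ((−1.96 − 0.75)/0.866) = 0.1% of those 1.5 SD younger. With correlation −0.3 the figures are 5.7% and 0.6%. With no correlation, both are 2.5%.

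**The case against.** The strongest reply is that SA2 asks for control values, not limits of normal. SA3 states their use, a comparison with normal subjects, which can be made without a reference interval. The title says only that the test is a potential one, no aim promises a cut-off, and the sentence about norms in Section 4 concerns rotational chairs. This stands as a reading of the words: SA2 does not literally commit to individual limits. It does not dispose of the point. If SA2 meant only a control mean for SA3, it would add nothing to SA3's own control group. Even that comparison needs a measure of spread, which Section 13 does not name.

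A reader might also infer three stronger claims that the documents do not support:

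- *That the plan yields nothing but group means.* Section 13 also names a single subject design. It measures the wrong thing for SA2 and cannot be run on one session, but it is there.
- *That the plan pools all ages.* Section 13 is silent on age. An age-specific analysis is unplanned, not excluded.
- *That the plan's limits would flag too many normal people.* The plan sets no limits. Mean ± 1.96 SD, percentiles and the observed range are methods an analyst might reach for; none is in the document.

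It is also fair to say that Section 13 has a larger problem, since its session comparison has no second session to use. The section needs rewriting for that reason anyway, and this point can be settled in the same revision.

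**Conclusion.** The point holds in limited form. Section 13 contains nothing that would turn 30 control scores into values against which a person could be judged: no spread, no reference interval and no use of age or sex for SA2. One of its two analyses needs a second session that Section 11 does not provide, and its group mean (95% CI about ± 0.37 SD) does not describe individuals.

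The need for limits follows from the title, the Background and the place of SA2 beside SA3, not from an explicit promise. The sizes assume normal scores, which a score bounded at 0 and 100 may not satisfy. The age percentages are illustrations under assumed correlations, not predictions. Limits can be obtained from 30 controls, but each is uncertain by about ± 0.6 SD near the average age and more at the extremes. They can only be provisional. The omission should be corrected, but it does not by itself prevent the SA3 comparison.

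**What to change.** In Section 13, add a paragraph for SA2:

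- Name the vergence value or values to be analysed. Check the distribution of the 0 to 100 score in the 30 controls and transform it if needed.
- Regress that value on age, with sex as a second term.
- Report the fitted mean, the residual SD and 95% prediction limits computed from the fitted model, so that the 27 df and the leverage at each age are used. Do not apply a flat multiplier of 1.96 or 2.08.
- Give a confidence interval for each limit and call the limits provisional. Do not use sample percentiles or the observed range as limits.

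In the same revision, reconcile the two-session analysis in Section 13 with the single session in Section 11.

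The cost is a paragraph and one regression on data already kept, with no extra subjects or visits. The downside is that the limits will be openly imprecise at n = 30.

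### Section 13 contrasts first with second sessions for every aim, although Section 11 gives each participant one session, and it states no mTBI-versus-control analysis for SA3

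*Combined protocol and SAP*

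**What the plan says.** **Aim and sample.** In Section 3, SA1 and SA2 concern normal subjects only. SA3 determines vergence values in subjects with a history of mTBI and compares them with normal values. Section 6 plans 30 controls and 30 mTBI patients.

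**Sessions.** Section 11 has two phases, controls and then mTBI participants. In each phase participants "undergo 1 session of vergence testing, along with a series of vestibular tests", and questionnaires follow that session. Section 10 ends a person's participation once the tests are done. Section 12, however, stores the "results of the vergence tests and vestibular testing done during the two sessions", and Section 13 states that "No PHI that can identify any subjects will be kept beyond the second session of testing".

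**Analysis.** Section 13 describes two analyses. For the group means, "In the group mean data scoring on each of the sessions will be aggregated for each of the specific aims", and then "First session scores will be compared to second session scores using standard statistical methods", with significance at p < 0.05. For the single-subject design, the plan takes the number of subjects, per test and per aim, "who have a significant difference in scores between the first and second session will be calculated", and describes it with descriptive statistics.

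**Data labels.** Section 11 says that de-identified data carry only sex and age. Section 12 adds a subject number linked to sex and age: "These results will be tied together by a subject number".

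**The concern.** Two faults meet in Section 13. First, its analyses presuppose two sessions per person, and the procedures section provides one. Secondly, whichever count is right, the contrast it describes is between sessions, while SA3 and the 30 + 30 recruitment call for a contrast between groups.

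SA3 is the aim that bears on the diagnostic question in the study's title. If Section 13 is followed as written, its p-value either has no data behind it or answers a session-to-session question. The method for the mTBI-versus-control comparison would then have to be settled outside the plan, possibly after the data have been seen.

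**Working it through.** **Step 1: the plan's own figure.** Section 6: 30 controls + 30 mTBI = 60, which agrees with the stated total. No power, effect size or standard deviation is given, so nothing further about the sample size can be reproduced.

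**Step 2: session count, side by side.**

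| Place | Sessions per participant |
|---|---|
| Section 11, controls | 1 |
| Section 11, mTBI | 1 |
| Section 10 | no return visit described |
| Section 12 | 2 |
| Section 13, comparison and single-subject count | 2 |
| Section 13, retention of identifying data | 2 |

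These entries cannot all describe one design.

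**Step 3: evaluable pairs.** A first-versus-second contrast within a person needs two scores on the same test.

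- One session: 60 subjects × 0 pairs = 0 pairs.
- Two sessions: 30 + 30 = 60 pairs at most, 30 in each group.

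**Step 4: what the contrast estimates with two sessions.** Suppose, for illustration, that the control mean is m at both sessions and the mTBI mean is m + D at both sessions.

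- Controls, second minus first: m − m = 0.
- mTBI, second minus first: (m + D) − (m + D) = 0.
- SA3's target, mTBI minus control: (m + D) − m = D.

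The session contrast is 0 whatever the value of D. A stable group difference, which is what SA3 looks for, cancels out of the planned comparison.

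**Step 5: does session mean phase?** If the first session meant the control phase and the second the mTBI phase, the group-mean sentence would become a between-group comparison. Two features of Section 13 count against this.

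- The aggregation and the contrast are laid down for each specific aim. SA1 and SA2 contain normal subjects only, so they have no second phase to compare.
- The single-subject count uses the same first-and-second-session terms for individuals whose own scores differ. No one belongs to both phases, so the terms there must mean repeat sessions of one person.

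**Step 6: is the group comparison stated elsewhere?** Section 14 adds only that the data of withdrawn subjects are not used and that these subjects are replaced. No other section describes a statistical comparison. SA3 names the comparison as an aim but gives no test or estimate for it.

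**The case against.** The strongest defence is the phase reading. Controls are tested in phase one and mTBI participants in phase two, with one session each, and Section 13 separates a group-mean analysis from a single-subject one. Taken alone, the group-mean sentence could then be a control-versus-mTBI test, and its p-value could be computed. The single-subject count by itself does not refute this for the group-mean sentence. The application to every aim does weigh against it, together with the use of the same terms for a per-subject count. What stands is that the investigators probably intend a group comparison, since SA3 says so. The fault is that the analysis text does not provide one.

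Three stronger claims are tempting and are not supported:

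- A reader might infer a multiplicity problem across the 17 tests in the Section 11 table. No passage plans 17 between-group tests, and Section 13's test-by-test wording belongs with the single-subject analysis, which is descriptive. No error rate is therefore claimed here.
- A reader might infer that several vergence endpoints compete for SA3. The table lists one vergence row, Vergence Pursuit, scored 0–100. What is open is how the multi-frequency response proposed in Section 4 relates to that score.
- A reader might take Section 18, which lets subjects see results after each session, as further proof of two sessions. That wording is compatible with one session per subject.

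**Conclusion.** The point holds and should be corrected before analysis. The documents contradict themselves on the number of sessions, and the only stated analysis does not deliver SA3's comparison of mTBI with normal subjects. Its size is 0 of 60 within-person pairs under Section 11, or up to 60 pairs under Sections 12 and 13, none of which gives an mTBI-versus-control contrast.

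The conclusion rests on reading the sections against each other. It needs no assumption about effect size, variance or abnormal rates. The stable difference D in the working is an illustration only.

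A reader might go further and infer that the study cannot answer SA3. The documents do not support that: one session in each of two groups of 30 yields the scores needed for a between-group comparison, provided that group membership is kept with the data. The defect lies in the analysis text and the stored labels, not in the testing itself.

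**What to change.** 1. Reconcile the number of sessions across Sections 11, 12 and 13.
2. In Section 13, make the SA3 analysis a comparison of the 30 mTBI and 30 control subjects as independent groups on one pre-specified vergence variable: either the 0–100 Vergence Pursuit score or one named summary of the multi-frequency response. Report the group difference with a 95% CI. Adjustment for age and sex, which are already recorded, is an option. Label the other listed tests exploratory.
3. Add group (mTBI or control) to the data held under the subject number. Sections 11 and 12 list only sex and age, and the SA3 analysis cannot be run from those labels alone.
4. If one session stands, delete the first-versus-second-session comparison and the single-subject count. If two stand, keep both as a separate within-subject analysis, and state which session's score enters SA3.

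**Cost.** If one session stands: protocol wording and one stored label, with no added subjects or tests. If two stand and only one is being run: up to 60 × 1 = 60 further sessions.
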